1.1 Background

Genital warts (condyloma) affect 100-200 per 100,000 adults annually. While 90% are caused by HPV types 6 and 11, high-risk HPV types can co-occur and increase dysplasia/carcinoma risk. Current treatments have significant limitations: imiquimod shows variable efficacy (28-56%), while electrocautery, despite high clearance rates (94%), causes discomfort and scarring.

1.2 Preliminary Data

Recent studies demonstrate that intramuscular administration of HPV vaccines (bivalent, quadrivalent, or nonavalent) can promote wart clearance. One study comparing intramuscular to intralesional bivalent HPV vaccine showed superior clearance with intralesional administration (81% vs 63%).

1.3 Rationale

Given the promising results with intralesional bivalent vaccine and the widespread availability of Gardasil 9 in the US, this study aims to assess intralesional Gardasil 9's effectiveness for treating genital condyloma.

2. Study Objectives

2.1 Primary Objective

To assess the efficacy of intralesional Gardasil 9 in treating genital condylomata through:

- Reduction in wart number
- Reduction in mean wart size
- Reduction in total skin area covered by warts

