2.2 Secondary Objectives

- Evaluate patient-centered outcomes using:
 - CECA (Specific Questionnaire for Condylomata Acuminata)
 - Dermatology Quality of Life Index (DLQI)
 - Global patient satisfaction (1-5 scale)
- Assess tolerability of intralesional Gardasil 9

3. Study Design

- Prospective, open-label, single-arm proof-of-concept study
- Duration: 12 weeks per participant
- Sample size: 10 participants
- Two treatment visits (Week 0 and Week 4)

4. Study Population

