4.1 Inclusion Criteria

- Age \geq 18 years
- Signed informed consent
- Minimum of 3 genital condylomata, each >3 mm in size

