5.1 Visit Schedule

Visit 1 (Week 0)

1. Informed consent
2. Baseline data collection:
 - Demographics
 - Medical history
 - Medication review
 - Condylomata history
3. Pregnancy test if applicable
4. Photography and measurements
5. Questionnaires (CECA, DLQI)
6. Shave biopsy ($\leq 5 \times 5 \text{ mm}$) for histologic confirmation
7. First Gardasil 9 injection
8. 15-minute observation period

Phone Follow-up 1 (Week 1)

- Assess adverse effects
- Arrange follow-up if needed

Visit 2 (Week 4)

1. Assessment of treatment response
2. Photography and measurements
3. Questionnaires (CECA, DLQI)
4. Second Gardasil 9 injection if indicated

5. 15-minute observation period

Phone Follow-up 2 (Week 5)

- Assess adverse effects
- Arrange follow-up if needed

Visit 3 (Week 12)

1. Final assessment
2. Photography and measurements
3. Questionnaires (CECA, DLQI, satisfaction)

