7.1 Sample Size

Pilot study of 10 participants; no formal sample size calculation as effect size is unknown.

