7.3 Primary Endpoint Analysis

Paired t-tests comparing baseline to week 12:

- Wart number
- Mean wart size
- Total skin area covered by warts

Significance level: $\alpha = 0.05$

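### The primary objective is worded as efficacy, but a single-arm test of zero change to Week 12 can only show that warts changed, not that the vaccine changed them

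*Combined protocol and SAP*

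**What the plan says.** Section 2.1 gives the primary objective as "To assess the efficacy of intralesional Gardasil 9 in treating genital condylomata through" reductions in wart number, mean wart size and total skin area covered. Section 1.3 speaks of effectiveness. Section 3 describes a "Prospective, open-label, single-arm proof-of-concept study", with "Duration: 12 weeks per participant". Section 7.1 adds: "Pilot study of 10 participants; no formal sample size calculation as effect size is unknown".

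For the three primary endpoints, section 7.3 specifies "Paired t-tests comparing baseline to week 12" at a significance level of 0.05. It does not say whether the tests are one- or two-sided, and it gives no rule for turning a p-value into a conclusion.

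Entry under 4.1 requires "Minimum of 3 genital condylomata, each >3 mm in size". Section 5.1 lists no separate screening visit. At Visit 1 it lists "Condylomata history" without itemising it, then photography and measurements, then a shave biopsy of up to 5 x 5 mm, then the first injection.

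The clearance figures in 1.2 (81% intralesional, 63% intramuscular, bivalent vaccine) are background. No analysis uses them as a comparator.

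**The concern.** A paired t-test against zero asks whether the average participant changed. It answers an efficacy question only if an untreated participant would, on average, not have changed. Nothing in the plan establishes that, and nothing measures or bounds the untreated change.

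Three non-vaccine influences are visible from the documents or the design. Warts may regress, grow or appear on their own over 12 weeks. The biopsy removes tissue after the baseline measurement, which can lower number, size and area unless the biopsied wart is handled separately. And participants enter only above a size and number floor, apparently judged at the visit that supplies the baseline, so some fall back toward the mean is expected.

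All three endpoints describe the same warts, so these influences can move them together. Agreement among the endpoints would not be independent confirmation. What is at stake is the reading of the main result: p<0.05 could be reported as efficacy for a treatment that did nothing.

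**Working it through.** **Inputs from the documents.** n = 10 (3, 7.1); paired t-test of baseline against Week 12 (7.3); alpha 0.05 (7.3). **Assumed:** two-sided testing and, in step 2, normally distributed changes. The documents give no SD, effect size or regression rate, and there is no sample-size calculation to reproduce.

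**1. What the test reacts to.** t = mean change / (SD of change / √10), with 9 degrees of freedom and critical value 2.262. The test is significant when mean change / SD exceeds 2.262 / √10 = 0.715, whatever caused the change. With no drift, the chance of a significant improvement is 2.5%.

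**2. Drift with no vaccine effect.** If the untreated mean improvement is d SDs of the change, t follows a noncentral t distribution with noncentrality d√10. The chance of a significant improvement is P(t > 2.262):

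| Assumed untreated drift d | d√10 | Chance of a significant improvement |
|---|---|---|
| 0.3 SD worsening | −0.949 | 0.2% |
| 0 | 0 | 2.5% |
| 0.3 SD shrinkage | 0.949 | 13% |
| 0.5 SD shrinkage | 1.581 | 29% |
| 0.8 SD shrinkage | 2.530 | 62% |

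**3. The same question on wart counts.** This is a simulation with an assumed baseline count of 3 + Poisson(4), no vaccine effect and 40,000 runs per case.
- If each wart regresses independently with probability 5%, 10% or 20%, a significant fall in wart number occurs in 25%, 70% or 98% of trials.
- If instead whole participants clear with probability 10%, 20%, 30% or 40% and the rest vary by at most one wart either way, it occurs in 2%, 11%, 29% or 53%.

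The answer therefore depends heavily on how regression happens. Rare whole-patient clearance leaves the rate near nominal.

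**4. Entry floor alone.** Two models, both with no true mean change:
- Selection on measured size above 3 mm (population mean 3 to 5 mm, between-patient SD 1.5 mm, measurement SD 0.3 to 1.0 mm): apparent shrinkage of 0.01 to 0.44 mm, and a significant fall in 3% to 15% of trials.
- Entry above the 30th or 50th percentile of a normal burden score, with baseline to Week 12 correlation 0.6 to 0.9: 5% to 19%.

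These inputs are also assumed. The effect runs in a known direction but is probably the smaller component, unless participants cluster near 3 mm or measurement is noisy.

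**5. Biopsy.** The order in 5.1 is measurement, biopsy, injection. The documents do not say whether the biopsied wart is counted at Week 12, so its contribution cannot be calculated.

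**The case against.** The strongest reply is that the design is openly declared. The study is called a single-arm proof of concept and a pilot, the effect size is said to be unknown, and nobody reading it would expect causal proof from 10 people. That stands as a defence of the single arm: it is a reasonable design for estimating change and describing tolerability, and this point does not ask for a control arm. It does not cover the combination of an efficacy objective with significance tests against zero, because neither label says how those p-values are to be read.

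A reader might infer that the plan defines efficacy as a significant fall, or commits itself to that conclusion. It does not. Section 2.1 has no significance criterion and 7.3 has no success rule. The link is a natural reading that the plan leaves open.

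A reader might also infer that the bias can only favour the vaccine. The documents do not support that. They contain no natural-history data, and 6.2 names worsening of condylomata among its stopping criteria, so movement the other way is contemplated. Step 2 shows that upward drift makes a false improvement rarer than nominal. Only the entry-floor component has a fixed direction by construction.

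Finally, small examples can overstate the ease of reaching significance. Four equal falls and six zeros give p = 0.037, but falls of 1, 2, 3 and 4 with six zeros give p = 0.063. Such examples say nothing about cause either way.

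**Conclusion.** The point holds as one about inference. With no control, run-in, stability requirement or benchmark, a significant fall from baseline cannot be attributed to the vaccine, and the efficacy wording in 2.1 goes further than the analysis in 7.3 can support.

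The size and net direction of the non-vaccine change are unknown. The 13%, 29% and 62% figures are conditional on assumed downward drifts of 0.3, 0.5 and 0.8 SD, and the 0.2% figure on an assumed upward drift of 0.3 SD. They show how strongly the result depends on an unmeasured quantity; they do not estimate this trial's error rate. Spontaneous change is likely to matter more than the entry floor, and the biopsy is a further contributor that cannot be quantified. The change is worth making before analysis, because it alters what the trial may conclude at almost no cost.

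**What to change.** 1. In 2.1, replace the wording about assessing efficacy with: *estimate the change from baseline to Week 12 after intralesional Gardasil 9*. Align the effectiveness wording in 1.3.
2. In 7.3, make the mean change with its 95% CI the primary result for each endpoint. State that p<0.05 against zero change will not be reported as evidence of efficacy, because non-vaccine change is not controlled. Say there also whether the biopsied wart is counted at Week 12.
3. Optionally, within the condylomata history already taken at Visit 1, itemise how long the current warts have been present and whether they were growing, stable or shrinking over the previous 12 weeks. Show each participant's Week 12 change against these items descriptively. The history may already cover part of this. The trend item relies on recall, and with 10 participants the display makes confounding visible but does not remove it.

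The cost is rewording and, if the option is taken, two form items and one display. No extra participants, visits or procedures are needed. The downside is a more modest claim.

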2.2 Secondary Objectives

- Evaluate patient-centered outcomes using:
 - CECA (Specific Questionnaire for Condylomata Acuminata)
 - Dermatology Quality of Life Index (DLQI)
 - Global patient satisfaction (1-5 scale)
- Assess tolerability of intralesional Gardasil 9

3. Study Design

- Prospective, open-label, single-arm proof-of-concept study
- Duration: 12 weeks per participant
- Sample size: 10 participants
- Two treatment visits (Week 0 and Week 4)

4. Study Population

4.1 Inclusion Criteria

- Age \geq 18 years
- Signed informed consent
- Minimum of 3 genital condylomata, each >3 mm in size

4.2 Exclusion Criteria

- Pregnancy or planning pregnancy
- Previous HPV vaccination
- Severe allergies to vaccine components
- Immunosuppressive medications/conditions
- Known HIV infection
- Leukemia or lymphoma

5. Study Procedures

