7.2 Analysis Populations

- Intent-to-treat (ITT): All participants receiving ≥ 1 dose
- Per-protocol: Participants completing study without major protocol deviations

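### Other wart treatment is barely restricted, not listed for recording after Visit 1, and has no analysis rule, so any reduction it adds would count as vaccine effect

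*Combined protocol and SAP*

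**What the plan says.** **Eligibility.** Section 4.1 asks for adult age, consent and a minimum number and size of warts. Section 4.2 excludes pregnancy, earlier HPV vaccination, vaccine allergy, "Immunosuppressive medications/conditions", HIV, and leukemia or lymphoma. The vaccination exclusion does bear on wart treatment, because Section 1.2 describes HPV vaccines as promoting clearance. Conventional treatments are not mentioned, and no interval since the last treatment is set.

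**Recording.** In Section 5.1, "Medication review" and the condylomata history are baseline items at Visit 1; the content of the history is not specified. Visits 2 and 3 list response assessment, photographs, measurements and questionnaires, and Visit 2 adds a possible second injection with observation. The phone calls cover adverse effects and arranging follow-up.

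**Analysis.** Section 3 describes a "Prospective, open-label, single-arm proof-of-concept study". Section 7.2 defines "Intent-to-treat (ITT): All participants receiving ≥ 1 dose", plus a per-protocol set that depends on major deviations, which are not defined. Section 7.3 specifies "Paired t-tests comparing baseline to week 12" for wart number, mean wart size and total area. Section 7.5 covers early discontinuation and missing data. None of these sections says what happens when a participant has used another wart treatment, and Section 6.2 does not list such use as a stopping criterion.

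**The concern.** The efficacy evidence is a within-person change with no comparator. A control arm would show how much change arises from treatment obtained elsewhere; here nothing does. A participant who uses another treatment and attends at Week 12 has neither discontinued nor gone missing, so Section 7.5 does not apply. The Week 12 values then enter the paired tests as they stand.

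The per-protocol set does not clearly help. Using a treatment that the protocol does not prohibit is not obviously a deviation, and nobody is asked to record it.

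There is opportunity for such use. Section 5.1 lists no contact between the Week 5 call and the Week 12 visit. Section 5.2 directs the injection to 3-5 index warts, while wart number and total area are primary endpoints, so a participant with more warts keeps uninjected lesions.

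What is at stake is mainly the effect estimate. Section 7.1 says "Pilot study of 10 participants; no formal sample size calculation as effect size is unknown", so a first estimate of the effect is a main product of the study.

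**Working it through.** The plan has no figure to reproduce: the sample size has no effect size, standard deviation or power behind it. The calculation below is an illustration of scale.

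**Inputs from the documents**
- n = 10, single arm (Sections 3 and 7.1).
- Paired t-test of baseline against Week 12, alpha 0.05 (Section 7.3). Sidedness is not stated; two-sided is assumed.
- Imiquimod efficacy 28-56% and electrocautery clearance 94% (Section 1.1).

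**Assumptions**
- The vaccine has no effect, so everything observed beyond noise comes from the other treatment.
- The Section 1.1 rates are read as the probability r of complete clearance.
- k of 10 participants use another treatment. The documents give no basis for k; 0 to 5 is an assumed range.

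**Step 1: shift in the estimate.** Expected mean percentage reduction in wart number = (k/10) × r × 100.

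For one user: 0.1 × 28 = 2.8 points, 0.1 × 56 = 5.6 points, 0.1 × 94 = 9.4 points.

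| Users k | r = 28% | r = 56% | r = 94% |
|---|---|---|---|
| 1 | 2.8 | 5.6 | 9.4 |
| 2 | 5.6 | 11.2 | 18.8 |
| 3 | 8.4 | 16.8 | 28.2 |
| 5 | 14.0 | 28.0 | 47.0 |

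**Step 2: effect on the test.** The paired t-test on wart number was simulated 40,000 times per setting. Further assumptions are a baseline count of 3 + Poisson(3) and a within-person change SD of 1 or 2 warts. The table gives the chance of a significant reduction; each range spans the two SDs.

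| Users k | r = 28% | r = 56% | r = 94% |
|---|---|---|---|
| 0 | 2.1-2.6% | 2.2-2.6% | 2.2-2.4% |
| 1 | 1.9-2.7% | 1.7-3.3% | 1.3-3.8% |
| 2 | 1.9-3.6% | 2.1-5.3% | 3.1-8.3% |
| 3 | 2.2-4.5% | 4.4-8.6% | 12.4-18.1% |
| 5 | 4.8-7.6% | 22.1% | 61.8-79.0% |

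The expected value without users is about 2.5%, half of 0.05. One or two users change this little, because one or two large changes among 10 raise the standard deviation of the differences along with their mean. The highest figure for two users is 8.3%. The estimate moves from the first user onward; the test moves materially only with several users of an effective treatment.

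**The case against.** The strongest reply is that this is a 10-person proof-of-concept study, that use of other treatment may be nil, and that the protocol is not silent. It excludes previous HPV vaccination, takes a condylomata history that may well cover past treatment, and photographs the warts at Weeks 0, 4 and 12. Section 1.1 says that electrocautery scars, so clinicians might notice it. Part of this stands:

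- **Prior treatment is partly covered.** A reader might infer that nothing about it is restricted or asked. The vaccination exclusion and the baseline history contradict that, although the history's content is unspecified and it does not reach beyond Visit 1.
- **Detection is not impossible.** A reader might infer that co-treatment could never be found. Photographs and examination may reveal a procedure. They are less likely to reveal a topical treatment, and a chance observation is not a record.
- **An inflated clearance rate cannot be calculated for this trial.** It is tempting to mix an assumed vaccine clearance rate with the 94%. The plan defines no clearance endpoint and gives no rate for intralesional Gardasil 9; the 81% and 63% in Section 1.2 are for the bivalent vaccine.
- **A favourable bias is not guaranteed.** It follows for a reduction added to whatever the vaccine does. If another treatment replaced the vaccine's effect, the direction could reverse: with two of 10 at 56% and the rest at 63%, (8 × 63 + 2 × 56)/10 = 61.6%, below 63%. Mean wart size can also move either way if only some warts are removed.
- **The ITT definition says only who is included.** That Week 12 values are used regardless of other treatment follows from the absence of any other rule, not from an explicit statement.

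What does not stand is the idea that the gap can be filled at analysis. The schedule as written does not collect the information, so the analyst could neither adjust for other treatment nor show that there was none.

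**Conclusion.** The point holds. Apart from previous HPV vaccination, current or recent wart treatment is unrestricted. No recording of it is listed after Visit 1, and the SAP has no rule for it. In this design, any reduction that another treatment adds is counted as vaccine effect and cannot be reliably separated later.

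The size is unknown because use is unknown. Under a null vaccine effect, with the Section 1.1 rates read as complete clearance, each user among 10 adds 2.8 to 5.6 points (imiquimod) or 9.4 points (electrocautery) to the mean percentage reduction in wart number. The t-test is little affected by one or two users under the assumed counts and SDs. The documents do not support saying that the trial's result will be biased, or that a false positive is likely. They support saying that the plan leaves no dependable means of ruling such bias out.

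**What to change.** **Section 5.1.** At Visits 2 and 3, add a question on other wart treatment since the last contact, covering both medication and procedures; a medication review alone might miss electrocautery. Specify that the baseline condylomata history captures current and recent treatment, with dates.

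**Section 4.2.** State whether current or recent wart treatment is permitted. Any restriction or interval is for the clinical team to set.

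**Sections 7.2 to 7.5.** Define use of other wart treatment as an intercurrent event. For wart number, mean wart size and total area alike, prespecify an analysis that does not credit measurements taken after it to the vaccine, and report it beside the as-observed result. One option is to use the last measurement before the other treatment. This fits the LOCF rule in 7.5 and keeps a genuine Week 4 response, which carrying the baseline value forward would erase. State also whether such use counts as a major deviation for the per-protocol set.

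**Cost.** One extra question at two existing visits, a fuller baseline history item and a few sentences of text. The estimate may come out less favourable, and using an earlier measurement may miss vaccine response that develops after it, which is a reason to show both results.

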5.1 Visit Schedule

Visit 1 (Week 0)

1. Informed consent
2. Baseline data collection:
 - Demographics
 - Medical history
 - Medication review
 - Condylomata history
3. Pregnancy test if applicable
4. Photography and measurements
5. Questionnaires (CECA, DLQI)
6. Shave biopsy ($\leq 5 \times 5 \text{ mm}$) for histologic confirmation
7. First Gardasil 9 injection
8. 15-minute observation period

Phone Follow-up 1 (Week 1)

- Assess adverse effects
- Arrange follow-up if needed

Visit 2 (Week 4)

1. Assessment of treatment response
2. Photography and measurements
3. Questionnaires (CECA, DLQI)
4. Second Gardasil 9 injection if indicated

5. 15-minute observation period

Phone Follow-up 2 (Week 5)

- Assess adverse effects
- Arrange follow-up if needed

Visit 3 (Week 12)

1. Final assessment
2. Photography and measurements
3. Questionnaires (CECA, DLQI, satisfaction)

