6.1 Adverse Event Monitoring

- Weekly phone follow-up after injections
- Documentation of local and systemic reactions
- Access to study clinicians for concerns
- Monthly research team meetings to review safety

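### The only scheduled pregnancy test is at Week 0, so no listed step would find an unrecognised pregnancy before the possible second injection at Week 4

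*Combined protocol and SAP*

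**What the plan says.** Pregnancy appears in three places in the combined protocol and SAP.

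- Section 4.2 (Exclusion Criteria) lists "Pregnancy or planning pregnancy".
- Section 5.1 (Visit Schedule) lists "Pregnancy test if applicable" as the third step of Visit 1, Week 0.
- Section 6.2 (Stopping Criteria) lists pregnancy, without saying how or when it would be detected.

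Section 3 (Study Design) provides for "Two treatment visits (Week 0 and Week 4"). At the second of these, Section 5.1 lists "Second Gardasil 9 injection if indicated" as the fourth step.

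**The concern.** The plan treats pregnancy as a reason not to dose, both at entry and during the study. At entry a test supports that rule. At Week 4 nothing listed does, so the rule relies on the participant already knowing that she is pregnant and saying so.

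Week 4 is the last dosing decision, and therefore the last point at which the stopping criterion can prevent an exposure that the investigators chose to avoid. The Week 5 call and the Week 12 visit come too late for that.

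The stake is participant safety, not inference: the endpoints and the analysis are the same either way. Sections 5.1 and 6.2 do not contradict each other, since a pregnancy known at Week 4 is dealt with by Section 6.2. The gap concerns only a pregnancy that has not been recognised.

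**Working it through.** **Step 1: the schedule.** The plan states no figure on this point, so the check is a reading of each contact up to the second injection.

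| Contact (Section 5.1) | Listed content | Pregnancy check? |
|---|---|---|
| Visit 1, Week 0, before the first injection | consent, baseline data, "Pregnancy test if applicable", photography and measurements, questionnaires, biopsy | Yes, conditional |
| Phone call, Week 1 | "Assess adverse effects"; arranging follow-up | No |
| Visit 2, Week 4, before the second injection | "Assessment of treatment response"; photography and measurements; CECA and DLQI | No |

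Other sections could add a check, but none does. Section 5.2 covers the anaesthetic, the dose and the injection site. Section 6.1 adds "Weekly phone follow-up after injections", recording of reactions, access to clinicians and team safety meetings. Section 9.1 covers anaesthetic, post-injection monitoring and emergency readiness. No contraception requirement appears in the available text.

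The count is 2 possible injections, 1 scheduled test, and 0 tests or questions about pregnancy between the first injection and the second.

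**Step 2: how many participants this could touch.** The sample size is 10 (Sections 3 and 7.1). The number of childbearing potential is not stated, so between 0 and 10 participants could be unchecked at Week 4.

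**Step 3: the chance of an exposure.** Let n be the number of participants of childbearing potential who receive the second dose, and p the chance that any one of them has an unrecognised pregnancy at Week 4. The documents give no value for p; the range 0.1% to 2% is an assumption. Treating participants as independent:

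- expected number exposed = n × p
- chance of at least one exposure = 1 − (1 − p)^n

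| n | p | Expected number | Chance of at least one |
|---|---|---|---|
| 0 | any | 0 | 0% |
| 5 | 0.1% | 5 × 0.001 = 0.005 | 1 − 0.999^5 = 0.5% |
| 5 | 2% | 5 × 0.02 = 0.1 | 1 − 0.98^5 = 9.6% |
| 10 | 0.1% | 10 × 0.001 = 0.01 | 1 − 0.999^10 = 1.0% |
| 10 | 2% | 10 × 0.02 = 0.2 | 1 − 0.98^10 = 18.3% |

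These figures measure exposure under the current schedule. They do not measure exposures that a repeat test would avert, which would be fewer.

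**The case against.** The strongest reply is that this is an outline protocol whose visit lists are not complete. Topical lidocaine is required by Section 5.2 but appears in neither injection visit, and Section 6.1 requires reactions to be documented although Visit 2 lists no such step. Absence from the Visit 2 list therefore does not prove absence from practice. That is fair as far as it goes. In both examples, however, another section states the requirement, and no other section states a Week 4 pregnancy check.

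A second reply is that the plan already has safeguards: those planning pregnancy are excluded, pregnancy is a stopping criterion, clinicians can be reached, and the second dose is given only if indicated. The exclusion does lower the probability. The other three can act only once a pregnancy is known, and the indication for the second dose is not defined in terms of pregnancy. Relying on a baseline test plus participant report is a coherent lighter choice, but it leaves the unrecognised case open.

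The objections to the size carry more weight:

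- The rate is assumed and spans a factor of 20.
- The 18.3% figure needs three extremes together: all 10 participants of childbearing potential, all 10 given the second dose, and the top rate.
- A test at Week 4 would also miss a very recent conception.
- For a pregnancy already present but undetected at Week 0, the test would avert only the repeat exposure, because the first dose has been given.

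All four stand. They limit the benefit that can be claimed, but they do not supply the missing step. Finally, the consent pages are not available and may carry contraception or reporting advice. That could lower the residual probability, though it would not be a scheduled test.

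**Conclusion.** The concern holds. Followed as written, the schedule could give the second dose to a participant with an unrecognised pregnancy, because the stopping criterion has no listed means of detection at that decision.

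The size is small. On the assumed range, the expected number exposed is at most 0.2. At the low end, which the exclusion of those planning pregnancy favours, the chance of any exposure is 1.0% or less. No size of harm is claimed, since the documents describe no specific maternal or fetal risk.

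The finding itself depends only on the listed steps, not on the assumed rate. The change is advisable because it is cheap and lets the plan's own rule operate, not because a large risk has been shown.

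**What to change.** In Section 5.1, Visit 2, add "Pregnancy test if applicable" as a step before "Second Gardasil 9 injection if indicated". State that a positive result means the injection is withheld under Section 6.2.

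The cost is one line in the visit list and one repeat of a test already used at Visit 1, in an unstated subset of the 10 participants, so at most 10 extra tests. It needs no new visit, staff or type of procedure, and does not change the sample size or the analysis.

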8.1 Data Collection

- REDCap electronic data capture
- Standardized photography with measurement software
- Secure storage of identifiable information

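### The baseline is measured before the Visit 1 shave biopsy and no rule excludes the biopsied wart, so tissue removed by the biopsy can count as vaccine response at Week 12

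*Combined protocol and SAP*

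**What the plan says.** Section 5.1 sets out Visit 1 as a numbered sequence. The relevant steps are "4. Photography and measurements", then (after the questionnaires) "6. Shave biopsy ($\leq 5 \times 5 \text{ mm}$) for histologic confirmation", then "7. First Gardasil 9 injection". No measurement is listed between the biopsy and the injection. The pregnancy test carries a qualifier but the biopsy does not, so the biopsy appears to be planned for every participant.

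Section 4.1 requires "Minimum of 3 genital condylomata, each >3 mm in size" and sets no upper size limit. Section 5.2 divides the injection among three to five index warts and places it just beneath the wart body.

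Section 7.3 specifies "Paired t-tests comparing baseline to week 12" for wart number, mean wart size and total area, at a significance level of 0.05. Section 3 describes a "Prospective, open-label, single-arm proof-of-concept study" with 10 participants.

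No section says which wart is biopsied, whether it may be an index wart, whether it counts towards the endpoints, or how a wart that has been removed is scored.

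**The concern.** The biopsy takes tissue off after the baseline has been fixed and before any vaccine is given. If the biopsied wart stays in the analysis, part of the change from baseline to Week 12 is surgical. With no control arm having the same biopsy, nothing in the design subtracts that part.

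All three affected measures are primary. One of the stated objectives is "Reduction in total skin area covered by warts", which any shave lowers unless the lesion grows back. For area, and for number after whole removal, the error favours efficacy. Because the biopsy is planned for everyone, the error is systematic and does not average out over participants.

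**Working it through.** The plan states no power, effect size or SD (section 7.1 gives no formal calculation), so there is no figure to reproduce. The check asks how large the distortion can be.

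**Inputs from the documents.** Biopsy up to 5 × 5 mm = 25 mm² (5.1); at least 3 warts, each over 3 mm (4.1); n = 10 (section 3, 7.1); α = 0.05 (7.3).

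**Assumptions.** Two-sided test; no vaccine effect; no regrowth by Week 12; SD of change in wart count 1, 1.5, 2 or 3.

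**1. Whole removal.** Losing one of k equal warts lowers number and area by 1/k: 33% for k = 3, 25% for k = 4, 20% for k = 5, 10% for k = 10.

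**2. Partial removal.** Take three round warts of 8 mm diameter. Each covers π × 4² = 50.3 mm², so the total is 150.8 mm². A 5 × 5 mm square has a diagonal of 7.07 mm and fits inside one of them. Share of area removed: 25 / 150.8 = 16.6%. The count is unchanged.

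**3. Mean size.** Take warts of 4, 6 and 8 mm (mean 6.0 mm) and remove the 4 mm wart whole.
- Dropped from the mean: (6 + 8)/2 = 7.0 mm, an apparent worsening.
- Scored as 0: (0 + 6 + 8)/3 = 4.7 mm, an apparent improvement.
- Total area: 91.1 to 78.5 mm², a fall of 13.8%.

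With 4, 4 and 4 mm, dropping the removed wart leaves the mean at 4.0 mm.

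**4. Paired t-test on wart number.** With df = 9 the critical value is 2.262. The noncentrality is √10 × (mean loss) / SD. Probability of rejecting when the vaccine does nothing (nominal 0.05):

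| Whole wart lost in | Mean loss | SD 1 | SD 1.5 | SD 2 | SD 3 |
|---|---|---|---|---|---|
| all participants | 1 | 0.80 | 0.47 | 0.29 | 0.16 |
| half | 0.5 | 0.29 | 0.16 | 0.11 | 0.08 |
| a quarter | 0.25 | 0.11 | 0.08 | 0.065 | 0.056 |
| none | 0 | 0.05 | 0.05 | 0.05 | 0.05 |

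Here the SD is that of the total change in count. If it is taken as natural change only and each participant loses a wart with probability 0.5, simulation gives slightly lower values for the half case: about 0.24, 0.15, 0.10 and 0.075.

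**5. After the fix.** With the biopsied wart out of both time points the artificial shift is zero. Simulated rejection is 0.049 at SD 1 and at SD 2.

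**The case against.** The case on the other side has several parts.

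- **The documents are silent; they do not say that the wart is counted.** This is correct, and the claim is only that it can be. But an analysis of wart number and total area with no stated exclusion includes it by default.
- **The 33% case conflicts with section 5.2.** A participant with exactly three warts who loses one whole has two left, while the injection needs three to five index warts. If 5.1 and 5.2 are read together, whole removal needs at least four warts and the largest loss is 25%. This is a fair limit on that illustration. It also shows that 4.1, 5.1 and 5.2 need reconciling. The 17% partial-removal example is unaffected.
- **The 0.80 stacks assumptions.** It needs whole removal in all 10 participants, no regrowth and an SD of 1. This stands: at whole removal in a quarter of participants the figures are close to nominal. No test is computed for area, because the documents give nothing from which to set its SD.
- **How an absent wart enters mean size is a wider gap.** It arises for every wart that clears. This also stands; the biopsy only guarantees that the question comes up where a wart is removed whole.
- **This is a small pilot, and spontaneous change is equally inseparable from a vaccine effect.** That is true, but spontaneous change cannot be removed without a control group. The biopsy artefact can be, by a rule on which wart is counted.

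**Conclusion.** The concern holds. Followed as written, the plan can credit tissue removed by biopsy to the vaccine. This is a bias in the primary comparison and goes beyond a missing detail. The order of steps and the absence of an exclusion rule are certain from the text; the size of the effect is not.

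Barring regrowth, the direction is favourable for total area after any removal and for wart number after whole removal. It is indeterminate for mean size. The illustrations run from no effect on the count (no wart removed whole) to a 25% or 33% fall in number and area (one of four or three equal warts removed). The corresponding false-positive rate for wart number runs from the nominal 0.05 to 0.80 under the most adverse assumptions shown. It should be fixed before the data are analysed.

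**What to change.** Mark the biopsied wart on the Visit 1 photograph. Exclude it from wart number, mean size and total area at baseline, Week 4 and Week 12. State the rule in 5.1 and 7.3.

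A weaker alternative is to define the primary baseline as a measurement made after the biopsy and before the injection. It removes the immediate loss, but the shaved remnant may still heal away or regrow by Week 12.

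Sections 4.1, 5.1 and 5.2 should also be reconciled on whether the biopsied wart may be one of the index warts.

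The cost is one sentence in each of 5.1 and 7.3 and one flag in the data capture form. Section 8.1 already provides for "Standardized photography with measurement software", so no extra visit is needed; the alternative adds one measurement at Visit 1. There are three downsides. The reported reductions become less favourable, by an amount that depends on each participant's wart count. A participant with three warts keeps only two evaluable lesions. A wart that was partly shaved and also injected drops out of the analysis.
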